7.6.4 Post-op Follow-up

Subjects will be seen between 5-21 days after the surgery for a post-op follow-up visit. The main purpose of this visit is to assess the subject for adverse events and obtain an x-ray. The following data will be collected and reported in the database:

- Adverse event assessment
- Pain medication usage
- X-ray independent radiologist will utilize imaging to assess X-ray data (defined in Section 7.3)

7.6.5 Follow-up: 3 Months and 6 Months

Subjects will be seen three months post op (\pm 21 days), and six months post-op (\pm 21 days). The main purpose of these visits is to assess the subject for adverse events and collect the data required to calculate all outcome measures (ASES, Constant score, Age Adjusted Constant Score, SANE, EQ-5D, subject satisfaction, pain). ROM and Strength tests are optional at both three and six month visits. X-rays are not completed at 3 months. The following data will be collected and reported in the database:

- Adverse event assessment
- Pain medication usage
- X-ray (6 month only) independent radiologist will utilize imaging to assess X-ray data (defined in Section 7.3)
- Subject Questionnaire
- ROM test (optional)
- Strength Test (optional)

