### 12.5.2. Sensitivity Analysis

Two separate sensitivity analyses will be completed on the primary endpoint, outlined below:

- 1) The primary effectiveness analysis will be repeated under the assumption that all subjects with missing endpoint data were successful.
- 2) The primary effectiveness analysis will be repeated under the assumption that all subjects with missing endpoint data were failures.
- 3) The primary effectiveness analysis will be repeated using multiple imputation for missing endpoint data. The covariates that may (list not all-inclusive) be included in the multiple imputation process are: age, gender, treated shoulder, arthritis diagnosis, Constant score (baseline and 12 month), and BMI.

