### 12.6.1. Constant-Murley Score

The Constant (Constant 2008) and adjusted Constant score (Constant 1986) will be summarized as part of the primary endpoint and as an inferential secondary endpoints. The Constant score is calculated as the sum of the following components:

- Average of 2 pain scores (15 points max):
  - Pain in shoulder normal activity: No=15, mild=10, moderate=5, severe=0
  - Linear 0-15 scale, where 0=no pain and 15=max pain, scored as the inverse of the scale: 15-(scale score); e.g., 15-0=15 (no pain contributes 15), 15-1=14,...,15-15=0 (max pain contributes 0).
- Sum of 4 activities of daily living questions (20 points max):
  - Occupation or daily living limited by shoulder: no=4, moderate=2, severe=0
  - Leisure and recreational activities limited by shoulder: no=4, moderate=2, severe=0
  - Sleep disturbed by shoulder: no=2, sometimes=1, yes=0
  - Highest level can use arm for reasonably painless activity: waist=2, xiphoid=4, neck=6, top of head=8, above head=10
- Sum of 4 ROM measure (40 points max):
  - o Forward flexion: 0-30=0, 31-60=2, 61-90=4, 91-120=6, 121-150-8, >150=10
  - o Abduction: 0-30=0, 31-60=2, 61-90=4, 91-120=6, 121-150-8, >150=10
  - External rotation: 2 points for each location reached (up to 10 points total)
  - Internal rotation: lateral thigh=0, buttocks=2, lumbrosacral junction=4, waist=6, 12th dorsal vertebra=8, interscapular region=10
- Power score (25 points max):
  - Average of 3 pulls (maximum of 25 pounds per pull) [Note: Statistician to verify pull was performed since some may say no but have 0 recorded.]

The average of three pulls were planned to be used to determine the strength component of the Constant score. In order to minimize missing data, the score will be calculated as long as at least one pull recorded. The average of the available pulls (1-3) will be used in the calculation.

Any combination of missing values that equate to a potential of >20 points would be excluded. For example, missing strength testing excludes a patient (if the subject was unable to complete the strength test then this would not exclude the patient); missing more than two of the ROM measures would exclude a patient; missing pain and one ROM test would exclude a patient, etc. For questionnaires missing partial data but not meeting the

exclusion threshold, missing responses are assumed to be worst case (contribute 0). Point details are as follows:

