- Pain (up to 15 points): only one of the two pain scores is required
- Activities of daily living: 4 questions; total of 20 points
- ROM: 4 tests; 10 points each
- Strength: Strength contributes 25% of the total score (>20% threshold).

The constant score adjustments will be made using Constant adjustment values in Table 1:

Age (y)	Male	Female
21-30	98	97
31-40	93	90
41-50	92	80
51-60	90	73
61-70	83	70
71-80	75	69
81-90	66	64
91-100	56	52

Table 1: Constant Score Adjustments

Apply the adjustment by dividing the score by the factor in the table, then multiplying by 100.

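### As listed, the multiple imputation of the primary endpoint has only baseline information for subjects lost before month 12, although questionnaires are mandatory at months 3 and 6

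*Protocol*

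**What the plan says.** The primary analysis uses ITT subjects whose 24-month status is known (Protocol 13.2.3). Under SAP 12.5.1, a subject without a 24-month Constant score or a readable 24-month radiograph is left out, unless a revision, a system-related serious adverse event or an unsuccessful implant already makes that subject a failure.

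Missing outcomes are examined in three ways (Protocol 13.2.4, SAP 12.5.2): all counted as successes, all counted as failures, and multiple imputation. For the imputation the SAP offers these covariates: "age, gender, treated shoulder, arthritis diagnosis, Constant score (baseline and 12 month), and BMI". It says that they may be used and that the list is not complete.

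The subject questionnaire is required at 3, 6, 12 and 24 months (Protocol Table 3 and 7.6.5; SAP 9). Protocol 7.6.5 gives as a main purpose of the 3- and 6-month visits to "collect the data required to calculate all outcome measures (ASES, Constant score, Age Adjusted Constant Score, SANE, EQ-5D, subject satisfaction, pain", then states: "ROM and Strength tests are optional at both three and six month visits".

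SAP 12.6.1 sets the scoring rule: "Any combination of missing values that equate to a potential of >20 points would be excluded". On strength it says: "missing strength testing excludes a patient (if the subject was unable to complete the strength test then this would not exclude the patient".

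**The concern.** The 12-month Constant score is the only post-operative covariate on the list. For anyone who leaves before month 12 it does not exist, so the listed model predicts that subject's outcome from age, sex, side, diagnosis, BMI and baseline Constant score. A subject who was recovering badly at 6 months and then left would be credited with roughly the success rate of a subject with the same baseline profile. The answers that show the poor recovery would already be in the database.

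The imputation is the one missing-data analysis between two deliberately extreme cases. When the extremes disagree, it is the one a reader will rely on.

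The statement in Protocol 7.6.5 about the Constant score is a separate and smaller matter. The visits are said to provide the score, while the tests that carry most of its points are optional.

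**Working it through.** **1. The plan's own figures.** Inputs (Protocol 13.2.2): null rate 0.85 − 0.10 = 0.75, assumed rate 0.85, one-sided alpha 0.025, power 80%, attrition 15%.

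n = [(1.960·√(0.75·0.25) + 0.842·√(0.85·0.15)) / 0.10]² = 132.07, rounded up to 133. Then 133 / 0.85 = 156.5, rounded up to 157. Both match the plan. Planned missing: 157 − 133 = 24 subjects.

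**2. What the listed model sees.**

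| Subject lost | Listed covariates available | Collected but not listed |
|---|---|---|
| Before month 3 | baseline only | none |
| After the 3-month, before the 6-month visit | baseline only | 3-month questionnaire |
| After the 6-month, before the 12-month visit | baseline only | 3- and 6-month questionnaires |
| After the 12-month visit | baseline and 12-month Constant | 3-, 6- and 12-month questionnaires |

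The documents do not give the share lost before month 12. As an assumed range, 0%, 50% and 100% of 24 give 0, 12 and 24 subjects, or 0%, 7.6% and 15.3% of 157.

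**3. Why the imputation matters.** Illustration with 113 successes among 133 completers (85.0%). The documents do not name the interval method, so the exact interval is used here.

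| Handling of the 24 missing | Rate | Lower 95% bound | Above 75%? |
|---|---|---|---|
| Excluded | 113/133 = 85.0% | 77.7% | yes |
| All failures | 113/157 = 72.0% | 64.3% | no |
| All successes | 137/157 = 87.3% | 81.0% | yes |

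On 157 subjects the lower bound first exceeds 75% at 129 successes (Wilson 129, Wald 128). That means 129 − 113 = 16 of the 24 (67%), or 15 by Wald. Variance between imputations would raise this somewhat.

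**4. Size of the bias.** This comes from simulation. Assumptions: 157 attempts; 15% missing; 50–70% of losses between the 6-month questionnaire and month 12; true success 80% or 85%; correlation with 24-month Constant change of 0.4–0.6 for the 6-month questionnaire and 0.75 for the 12-month Constant score; odds of loss 2 to 3 times higher per SD worse.

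- Baseline plus 12-month Constant: success overstated by about 0.5 to 2 points.
- Adding one 6-month questionnaire score: 0.15 point or less remains.
- With true success 80%, early losses succeed 62–73% of the time but are credited with about 80%.

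Rough check for the 80% case: 12 early losses × 0.07 = 0.84 subjects, and 0.84/157 = 0.5 point. At the other end, 24 × 0.70 = 16.8 early losses × 0.18 = 3.0 subjects, and 3.0/157 = 1.9 points.

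The mechanism of loss decides the result. If loss is unrelated to outcome, there is no bias. If it depends directly on the unseen 24-month outcome, adding the questionnaire removes only a small part.

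**5. Constant score at 3 and 6 months.** Weights (SAP 12.6.1): pain 15, daily activities 20, ROM 40 ("ROM: 4 tests; 10 points each"), strength 25 ("Strength: Strength contributes 25% of the total score (>20% threshold").

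- Strength not done: 25 points missing, above 20, no score.
- All ROM not done: 40 missing, no score.
- Both not done: 65 missing, no score; 35 questionnaire points remain.
- One or two ROM tests not done, all else present: 10 or 20 missing, still scored.

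**The case against.** **The list is open.** The SAP does not exclude 3- and 6-month data, and a reader might infer that it does. The wording permits the better model. It equally permits leaving those data out, and it leaves the choice open until outcomes are known. By contrast, SAP 13.2 fixes its propensity covariates and gives model building to a statistician without access to outcomes.

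**The optional tests are not the cause.** A reader might infer that the imputation gap arises because ROM and strength are optional. It does not. Making them mandatory would leave the listed covariates unchanged, and the omitted questionnaire is already mandatory.

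**The size rests on assumptions.** This stands. The documents give 15% attrition without timing or mechanism. The simulated window is the one where a 6-month score helps most, and if loss depends on that score, conditioning on it must remove the bias. Known failures are not imputed, so some of the worst early outcomes never reach the model. The simulations are not known to have removed them first.

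**The primary result is untouched.** This also stands. A reader might infer that the trial's conclusion is biased, but the imputation is one of three sensitivity analyses and the all-failures case is reported beside it. Nor should the bias be set against the complete-case bar of 110/133, because imputed data are judged on 157 subjects.

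**Protocol 7.6.5 has no inferential consequence.** Correct. The tests concern 24 months, and endpoint components are tabulated at 12 and 24 months only (SAP 12.5.1). A reader might also infer that the early Constant score will often be missing. No document gives a rate at which the tests are skipped, and subjects unable to do the strength test are still scored.

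**Conclusion.** The point holds in limited form. On the covariates the SAP names, the imputation has only baseline information for subjects lost before month 12, while relevant scores are collected from every subject who attends at months 3 and 6.

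If loss tracks early recovery, the overstatement is roughly 0.5 to 2 percentage points (0.8 to 3.1 of 157 subjects) under the stated assumptions. It would change the reading only if the imputed total lay within about three subjects of the 129 needed. The bias is zero if loss is unrelated to outcome, and most of it stays if loss depends directly on the unseen 24-month outcome.

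This weakens a sensitivity analysis, not the primary analysis. It is still worth correcting, because this is the only analysis between the two extremes and the better model needs no new data. The inconsistency in Protocol 7.6.5 is real but is a matter of wording.

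**What to change.** In SAP 12.5.2 item 3:

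- Pre-specify a small, non-redundant set of 3- and 6-month questionnaire scores, for example ASES and SANE, or the 35-point Constant pain and daily-activity subscore, beside the covariates already listed. VAS pain is already part of ASES (SAP 12.6.2), so it need not be added to it.
- Impute missing 24-month Constant change as a continuous variable, then apply the 17-point cut.
- Impute a missing 24-month radiographic component separately, since the cut covers only one of the four components.
- Keep revisions, system-related serious adverse events and unsuccessful implants as failures, as SAP 12.5.1 requires.

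Separately, state in Protocol 7.6.5 that Constant and adjusted Constant scores exist at 3 and 6 months only when the optional tests done satisfy the SAP 12.6.1 scoring rule.

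Cost: SAP and protocol wording and slightly more modelling work, with no new visits, tests or subjects. Overlapping scores could cause collinearity, which a small set avoids. Subjects lost before month 3 gain nothing from the change.

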7.6.6 Follow-up: Annual

Subjects will be seen 12 months post-op (\pm 42 days), 24 months post-op (\pm 42 days), and annually thereafter until the last implant attempt subject completes their 24 month post-op visit or determined lost to follow-up. Annual visits, after 24 months, will have a window of \pm 84 days. The main purpose of the these visits is to assess subjects for adverse events and collect the data required to calculate all outcome measures (ASES, Constant score, Age Adjusted Constant Score, SANE, EQ-5D, subject satisfaction, pain). The following data will be collected and reported in the database:

- Adverse event assessment
- Pain medications
- X-ray independent radiologist will utilize imaging to assess X-ray data (defined in Section 7.3)
- Subject Questionnaire
- ROM test
- Strength test

Subjects may be asked to return for additional visits after the study is completed, if deemed necessary.

7.6.7 Follow-up: Pre-Operative Screen Failures

Reason for the pre-operative screen failure will be documented on the eligibility form and then the subject will be exited.

7.6.8 Follow-up: Intra-Operative Screen Failures

Reason for the intra-operative screen failure will be documented on the eligibility form. Subjects will be seen at 12 and 24 months to gather available safety information. These visits may occur over the phone if the subject is unable to attend in person. Subjects will be exited after the 24 month visit.

7.6.9 Follow-up: Unsuccessful Implant Attempt

Reason for the unsuccessful implant attempt will be documented on the surgical form. Subjects will be seen at 12 and 24 months to gather available safety information. These visits may occur over the phone if the subject is unable to attend in person. Subjects will be exited after the 24 month visit.

7.6.10 Follow-up: Revisions

If a subject has revision surgery, the subject shall remain in the study and complete all required follow-up visits.

7.6.11 Follow-up: Explants

Subjects who have the Pyrocarbon HH explanted shall remain in the study and complete annual follow-up visits to gather available safety data

7.7 Additional Data Collection

Subjects may call or visit the investigative site at times other than for required study visits. It is only required to notify Tornier if the visit or phone call is associated with an adverse event, revision, device explant, reoperation, device malfunction, subject death, or study exit. Data associated with these events must be documented and reported in the database on the associated eCRFs.

Revision and Device Explants

A revision is a procedure that adjusts or in any way modifies or removes any component of the original implant configuration, with or without replacement of a component, after the initial surgery. A revision may also include adjusting the position of the original configuration.

An explant is a revision that includes permanent removal of any system component. If a subject has a revision that includes an addition of a glenoid component (revision to TSA) the Pyrocarbon humeral head must be permanently explanted.

All explanted system components, including the Pyrocarbon HH devices and stems, must be returned to Tornier for analysis per the system retrieval and analysis protocol in Appendix 4.

Reoperation

A reoperation is any invasive procedure to the affected shoulder that does not include removal, modification or addition of any components to the original implant configuration (e.g., drainage of a hematoma at the surgical site). Subjects will not be considered a failure solely due to a reoperation and will follow their original follow-up schedule.

Device Malfunction

All failures and malfunctions of the implant system must be reported to Tornier as soon as possible. In the event of a system malfunction, every effort must be made to return the suspected system to Tornier for analysis.

Death

During the study, all deaths must be reported to the Sponsor within 10 working days of the study personnel's knowledge of the death. A copy of death records, medical records for the events that led to the subject's death, death certificate (if available) and an autopsy report (if performed) must be sent to the Sponsor as soon as they become available.

7.8 Study Exit

Subjects will exit the study after the last subject with an implant attempt completes their 24 month followup visitor is determined lost to follow-up. Reasons for exiting a subject early may include:

- Subject voluntary withdraw of participation
- Investigators may withdraw subjects from the study if the investigator feels it is in the subject's best interest to withdraw or if the subject demonstrates non-compliance to the CIP.
- Death
- Subject lost to follow-up.
- It was determined that subject did not meeting inclusion/exclusion criteria prior to surgery (preoperative screen failure)

In the case that the subject is determined to be lost to follow-up, at least three documented attempts must be made to contact the subject and at least one of the attempts must be in writing via certified letter. Subjects who exit the study prior to study completion will not be replaced.

8 Investigational Device Handling and Traceability

The Ascend Flex System stems and associated instruments are not investigational and will not require tracking while at the investigative site. When the Pyrocarbon HH is paired with the Ascend Flex stem, and implanted in the body, the system (Pyrocarbon HH and Ascend Flex Stem) are both considered investigational and require tracking.

The Pyrocarbon HH is investigational and will be tracked from the time it is shipped from Tornier until it is either implanted into a study subject, or returned to Tornier after completion of the enrollment. A Device Accountability Log will be maintained at each study site and will be provided by Tornier in the Regulatory Binder. Devices allocated for investigational site use will be recorded in the Device Accountability Log upon delivery to the study site and will be stored in a secured area until use. No devices will be shipped to an investigative site until the site receives IRB approval to conduct the study. Each site will be responsible for tracking the receipt and disposition of all study devices. All unused study devices must be returned to Tornier.

The Device Accountability Log will be updated as devices are received, opened, used or returned. It will contain: receipt dates of devices and their lot or serial numbers; subject study identification number and their implant dates; and dates devices were returned to Tornier, along with the reason for the return.

9 Study Deviations

A study deviation is defined as an event within a study that did not occur according to the CIP or the CTA. Prior approval by the Tornier Clinical Study Manager is expected in situations where the investigator anticipates, contemplates, or makes a conscious decision to deviate. Prior approval is not required when a deviation is necessary to protect the life or physical well-being of a subject in an emergency or in unforeseen situations beyond the investigator's control (e.g., subject failure to attend scheduled follow-up visits, inadvertent loss of data due to computer malfunction, etc.). All study deviations must be reported regardless of whether medically justifiable, pre-approved by Tornier, an inadvertent occurrence, or done to protect the subject in an emergency. The deviation must be recorded with an explanation for the deviation. Reporting of deviations must comply with IRB policies, local laws, and/or regulatory agency requirements. An investigator shall notify Tornier and the reviewing IRB of any deviation from this CIP taken to protect the life or physical well-being of a subject in an emergency. This must be given as soon as possible, but in no event later than 5 working days after the emergency occurred. Tornier is responsible for analyzing deviations, assessing their significance, and identifying any additional corrective and/or preventive actions (e.g. amend the CIP, conduct additional training, etc.). Repetitive or serious investigator compliance issues may require initiation of a corrective action plan with the investigator, and in some cases, necessitate suspending site enrollment until the problem is resolved or ultimately terminating the investigator's participation in the study.

10 Adverse Events

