13.2.2 Sample Size

Statistical considerations for powering the primary endpoint include the following:

- 80% power with a one-sided 0.025 level of significance
- Non-inferiority test of one proportion
- 10% non-inferiority margin, and performance goal of 85%
- Assumed success rate of 85%
- Attrition rate of 15%

The sample size for this endpoint was calculated using SAS (Version 9.3) under a one-sided z-test of a binomial proportion. The minimum required sample size is estimated using the above list of statistical considerations. The resultant sample size under these assumptions is 133 subjects with an implant attempt and evaluable endpoint data. With 15% attrition, 157 total implant attempts are needed. Up to 190 subjects may be enrolled to account for pre and intra-operative screen failures. Enrollment will stop once 157 subject have had an implant attempt.

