13.2.3 Analysis

The number and proportion of subjects reaching the composite success outcome will be summarized. Additionally, a 95% confidence interval (CI) will be calculated for the proportion. The non-inferiority of the test system to the performance goal will be evaluated using the 95% CI for the observed test system success rate. The study will be considered a success if the lower bound of the confidence interval is greater than 75% (85% - 10%).

The primary analysis will be based on the ITT population with available 24 month data. A supportive analysis based on the PP population will also be presented. The impact of missing 24 month data will be evaluated through sensitivity analyses, described in the next section.

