### 12.5. Primary Effectiveness Analysis

### 12.5.1. Primary analysis

The primary endpoint is the rate of patient success at 24 months. A subject is a success at 24 months if:

- Their change in Constant score is  $\geq 17$  and
- They did not have revision surgery; and
- There is no radiographic evidence of system disassembly or fracture, and
- They did not have a system-related serious adverse event.

Subjects that undergo revision surgery within 24 months will be considered a primary endpoint failure at the time any component of the system is revised.

If a subject is missing the 24 month radiographic evidence assessment or Constant score component of the composite endpoint and did not have a system-related SAE or revision surgery, they will be excluded from the primary analysis due to inability to claim success or failure.

Subjects in whom an implant was attempted but the implant was unsuccessful will be included as failures in the primary analysis, regardless of the availability of 24 month radiographic evidence assessment or Constant score.

The presence of radiographic evidence of system disassembly or fracture will be assessed by independent radiologists. Discrepancies among the independent evaluations will be settled by majority rule. If the radiologists are unable to assess or the image wasn't available at 24 months, this will be considered missing data and the subject will be excluded from the primary analysis.

The non-inferiority of the test system to the performance goal will be evaluated using the 95% CI for the observed test system success rate. The study will be considered a success if the lower bound of the confidence interval is greater than 75% (85% - 10%).

The number of subjects who are successes (X) for each of the 4 individual components of the composite success endpoint, along with the number evaluated (N), will be summarized at 12 and 24 months as (X/N) and displayed with the overall success endpoint results based on data up to 12 and 24 months.

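### Protocol 7.8 lets an unblinded investigator withdraw a subject for non-compliance after an implant attempt, which can take some failures out of the primary denominator

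*Protocol*

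**What the plan says.** Protocol 7.8 (Study Exit) lists the reasons for early exit. One is withdrawal by the investigator in the subject's best interest "or if the subject demonstrates non-compliance to the CIP". The clause does not define non-compliance, is not confined to the time before surgery, needs no sponsor or independent review, and does not ask for 24-month data afterwards. The same section says: "Subjects who exit the study prior to study completion will not be replaced". It requires three documented contact attempts before a subject is declared lost to follow-up, but sets no comparable step for investigator withdrawal.

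Protocol 13.2.3 says: "The primary analysis will be based on the ITT population with available 24 month data". SAP 12.5.1 says of subjects who lack the 24-month Constant score or radiographic assessment, and who had no system-related SAE or revision, that "they will be excluded from the primary analysis due to inability to claim success or failure". It keeps unsuccessful implant attempts in as failures whatever data are available. SAP 9.2 states that there is no blinding.

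Study success is defined only by the lower bound of the 95% confidence interval in the primary analysis exceeding 75% (Protocol 13.2.3, SAP 8).

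**The concern.** After a one-time implantation there is no continuing study treatment to stop, so non-compliance gives no evident reason to stop observing the subject. Protocol section 9 already treats departures from the plan as deviations and names failure to attend scheduled visits as an example. Elsewhere the protocol keeps subjects under observation: revised and explanted subjects remain in the study (7.6.10, 7.6.11), and unsuccessful attempts are followed to 24 months (7.6.9).

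The withdrawal decision is discretionary, is made after treatment, and is taken by someone who knows how the shoulder is doing. If non-compliance goes with a poor result, which is plausible but not documented, the success rate is estimated in a favourably selected group although the analysis is labelled ITT. Withdrawal also ends planned safety follow-up of a permanent investigational implant.

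**Working it through.** **1. The plan's own sample size.** The inputs, from Protocol 13.2.2, are "80% power with a one-sided 0.025 level of significance", a performance goal of 85% with a 10-point margin (so p0 = 0.75), an assumed success rate p1 = 0.85, and a calculation "under a one-sided z-test of a binomial proportion".

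n = [(1.960 × √(0.75 × 0.25) + 0.842 × √(0.85 × 0.15)) / 0.10]² = [(0.8487 + 0.3005) / 0.10]² = 132.07, so 133.

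With 15% attrition, 133 / 0.85 = 156.5, so 157. Both stated figures reproduce. The plan thus allows for 157 − 133 = 24 non-evaluable subjects from all causes.

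**2. Who can leave the denominator (SAP 12.5.1).**

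| Status of a withdrawn subject without 24-month Constant score or X-ray | Primary analysis |
|---|---|
| Prior revision | stays, failure |
| Prior system-related SAE | stays, failure |
| Unsuccessful implant attempt | stays, failure |
| Would have had a Constant change below 17, none of the above | excluded |
| Radiographic failure, none of the above | excluded |

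**3. Illustration in counts.** Assumptions: 157 attempts, no other loss, and only failures leave. The plan does not name the interval method, so results are given for the exact (Clopper-Pearson) bound, with the Wald count alongside.

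| Successes of 157 | Exact lower bound, all counted | Failures removed to pass, exact (Wald) | Exact lower bound after removal |
|---|---|---|---|
| 126 (80.3%) | 73.2%, fail | 4 (2) | 126/153: 75.4% |
| 124 (79.0%) | 71.8%, fail | 6 (5) | 124/151: 75.1% |
| 118 (75.2%) | 67.6%, fail | 14 (12) | 118/143: 75.3% |

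With all 157 counted, 129 successes are needed to pass (Wald 128), so 126 is a near miss and 118 sits at about the null rate. Four removals are 4/157 = 2.5% of attempts and 14 are 14/157 = 8.9%.

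**4. Type I error under outcome-related exit.** True success rate 75%, 157 attempts. The documents give no exit rates by outcome, so those below are assumed. They cover exit by every route, not non-compliance alone.

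| Exit rate, failures / successes | Type I error, exact (Wald) |
|---|---|
| 15% / 15% | 0.020 (0.037) |
| 20% / 15% | 0.038 (0.067) |
| 25% / 15% | 0.070 (0.117) |
| 30% / 15% | 0.121 (0.190) |
| 24% / 12% (total 15%) | 0.087 (0.138) |
| 30% / 10% (total 15%) | 0.191 (0.273) |

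**5. What the worst-case analysis can tell.** At the design rate with 24 missing, 113/133 = 85.0% has an exact lower bound of 77.7% and passes. Counting the 24 as failures gives 113/157 = 72.0%, lower bound 64.3%, which fails. To pass that analysis, 129 of the 133 observed subjects (97.0%) would have to succeed.

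**The case against.** The strongest reply is that the plan already exposes the problem. Protocol 13.2.4 and SAP 12.5.2 repeat the primary analysis with all missing subjects as successes, with all as failures, and with multiple imputation that may use the 12-month Constant score. SAP 12.3 tabulates reasons for early withdrawal, and Protocol 7.7 requires study exits to be reported. Protocol 12.2 makes failure to follow subjects to schedule a possible ground for terminating a site, which discourages dropping them. Protocol 2.2 says that subjects with a successful implant attempt will be followed for at least 24 months.

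This stands in part: selective withdrawal would be visible. But none of these analyses decides study success. The worst-case run would very probably fail at the planned attrition even if exits were harmless (step 5), so it cannot separate harmless from selective exits. The covariates listed for imputation, which are not exhaustive, do not include the reason for withdrawal.

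Two further points stand in full. The denominator effect comes from the complete-case rule, so voluntary withdrawal, loss to follow-up, death and best-interest withdrawal have the same effect; the non-compliance ground differs in being discretionary and easily removed. And rehabilitation is a modifiable guideline (Protocol 7.6.3), so missed rehabilitation is not clearly non-compliance.

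A reader might infer that any likely failure can be removed. SAP 12.5.1 does not support that, because revisions, system-related SAEs and unsuccessful attempts stay in. A reader might also start from 133 evaluable subjects and treat four further removals as lying within the planned 15%. They do not: 133 already uses up that allowance, and four more would leave (24 + 4)/157 = 17.8% missing.

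**Conclusion.** The concern holds as a possible bias through a discretionary exit clause, limited to Constant-score failures and to radiographic failures without a revision or system-related SAE. Its size cannot be stated, because the documents give no count of withdrawals for non-compliance. In the illustration, four removals reverse a near miss at 126/157 and 14 are needed at 118/157 (Wald 2 and 12). Those counts assume no other loss and that no success is ever withdrawn. The type I error figures rest on assumed exit rates.

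The documents do not show that the clause was misused or that a given verdict would change, and the sample size is not in question. The change should be made because it is cheap and closes an avoidable route out of the only analysis that decides success.

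**What to change.** In Protocol 7.8, for subjects with an implant attempt, delete the non-compliance ground for investigator withdrawal. Record non-compliance as a deviation under section 9. Keep the subject in scheduled follow-up, and keep seeking the 24-month Constant score, X-ray and adverse-event status unless the subject withdraws consent, dies or is lost to follow-up. Leave the best-interest ground in place, but seek 24-month status with the subject's agreement.

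The cost is a short protocol edit, some extra contact effort at sites and more deviations to log. The change reduces the bias but does not remove it: subjects who do not return remain missing, and the complete-case rule still applies to them.
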